## **METHODS**

Subjects will be randomized 1:1 to receive usual insulin treatment of six injections daily (Humalog® injected three times daily before meals plus Humulin N® insulin injected at 8am, 4pm and midnight) as diagrammed in Figure 1, or 3 injections of Humalog® Mix50/50™ (injected only before meals) as diagrammed in Figure 2.

Baseline measures will include glucose tolerance test data, height, weight, and A1C by DCA2000+. In addition to the standard instruction to test blood glucose pre- and one-hour postprandial, all participants will be asked to test blood glucose levels at 3 a.m. Patients on the Humalog® Mix50/50™ arm of the study will be initially prescribed insulin doses of 0.3 times their weight in kilograms to be taken before each of three meals. Those on the standard therapy arm will be initially prescribed insulin doses calculated at 0.15 times their weight in kilograms for each of their 6 injections.

---

 We shall use American Diabetes Association criteria for diagnosis of GDM: blood glucose concentration >140 mg/dL one hour after administration of a 50 gram glucose load, followed by an oral glucose tolerance test (OGTT) in which 2 or more of the readings are at or above 95 mg/dL fasting, 180 mg/dL at one hour, 155 mg/dL at 2 hours and 145 mg/dL 3 hours after administration of a 100 gram glucose load (12).

Participants will be seen weekly for adjustment in dosages based on their food records, downloaded glucose monitor data and A1 C levels. Subjects in the study group whose fasting glucose exceeds 90 mg/dl will be prescribed Humalog® Mix75/25™ at their evening meal rather than Humalog® Mix50/50™. Subjects will be discontinued from the study if their 3 a.m. blood glucose concentration falls below 55 mg/dL that is unresponsive to a snack at bedtime or if their fasting blood glucose is greater than 90mg/dL despite increasing doses of Humalog® Mix50/50™ at the evening meal followed by treating with Humalog® Mix75/25™ at the evening meal.

Maternal weight will be recorded at each visit. Participants will be asked to bring their supply of insulin pens to every other visit, for which they will be paid ten dollars to maximize cooperation with this essential aspect of the research. The insulin pens will be counted as measures of adherence.

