## **SAMPLE SIZE**

40 women will be recruited into the study in order to achieve at least 30 evaluable subjects (15 in each treatment arm) over the 12 months duration of the study. Based on the standard deviation for fasting glucose concentrations reported from the NHANES II study, measurable data from 30 subjects (15 in each group) will have 80% power to find an inter-group difference as small as 8 mg/dL at a p-value of 0.05 (13).

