## **STATISTICAL ANALYSIS**

Data analysis will be done using SAS for Windows version 9. Differences between groups in continuous variables (glucose, A1C, birth weight etc.) will be compared with t-tests and potential confounders (age, race/ethnicity etc.) will be controlled for with linear regression. Differences in categorical variables (hypoglycemic events, macrosomia, type of delivery

etc.) will be evaluated using chi-square or Fisher's tests as appropriate. Our tests will be testing the hypothesis that the two treatments are different and the null hypothesis will be equivalence.

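### For uncommon yes/no outcomes at 15 women per arm, the chi-square-or-Fisher choice will usually mean Fisher's test and gives up about 10 to 15 points of power that an exact unconditional test would keep

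*Protocol*

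**What the plan says.** The protocol's Statistical Analysis section lists hypoglycemic events, macrosomia and type of delivery as examples of categorical variables, and says that differences in them "will be evaluated using chi-square or Fisher's tests as appropriate". It gives no rule for choosing between the two tests, and no significance level, event rate or target difference for these outcomes. The same section adds: "Our tests will be testing the hypothesis that the two treatments are different and the null hypothesis will be equivalence".

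The Sample Size section says that "40 women will be recruited into the study in order to achieve at least 30 evaluable subjects", which is 15 per arm. Under Methods, "Subjects will be randomized 1:1". The only significance level in the document belongs to the fasting glucose power statement, for a difference "as small as 8 mg/dL at a p-value of 0.05".

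Maternal hypoglycemia and neonatal outcomes are secondary objectives. The primary measure is fasting glucose.

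**The concern.** At 15 per arm, Fisher's test can reject only on quite extreme tables, so its true error rate lies well below the nominal 5%. The comparisons most exposed are the uncommon harms that the protocol itself wants to look at: macrosomia, neonatal hypoglycemia and, if scored as any or none per woman, nocturnal hypoglycemia. The Rationale names nocturnal hypoglycemia as the possible drawback of the premix, and Anticipated Findings asks for its careful assessment.

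At stake is a cluster of events in one arm that the same 30 women could show at a guaranteed 5% error rate but that the planned test would call non-significant. Because the investigators expect the regimens to be equivalent or non-inferior, a non-significant result is also easily read as support for that expectation.

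**Working it through.** **Inputs.**
- From the protocol: 15 evaluable women per arm as the planned minimum, up to 20 if all 40 are evaluable, and 1:1 allocation.
- Assumed, because the protocol does not give them: a two-sided 5% level for these tests; Fisher if any expected count is below 5, otherwise uncorrected chi-square; and every event rate below.

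The only power figure in the plan (80% for fasting glucose) concerns another outcome, so there is no stated figure to reproduce here.

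**When Fisher applies.** With m events among 30 women in equal arms, the expected counts are m/2 events and (30 − m)/2 non-events per arm. One of them is below 5 when m < 10 or m > 20. At a common rate of 10% this is essentially certain; at 15% it happens 99% of the time.

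**Size and power.** For a rejection region R, the rejection probability is the sum over (a, b) in R of Bin(a; 15, p1) × Bin(b; 15, p2). Size sets p1 = p2, and the maximum is taken over that common rate.

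| Procedure | Maximum size, 15 v 15 | Maximum size, 20 v 20 |
|---|---|---|
| Fisher on every table | 1.8% | 2.5% |
| Mixed rule (the plan, as assumed) | 4.3% | 5.2% |
| Boschloo | 4.3% | 4.6% |

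At 15 v 15 the mixed rule's size depends strongly on the common rate: 0.6% at 10%, 1.3% at 15%, 1.9% at 20%, 2.9% at 30% and 3.9% at 40%.

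**Which tables differ at 15 v 15.** Boschloo's region is all tables with Fisher p ≤ 0.0996. It contains everything the mixed rule rejects, plus two patterns and their mirror images:
- 0 v 4 events: p = 2 × C(15,4)/C(30,4) = 2 × 1365/27405 = 0.0996.
- 1 v 6 events: p = 2 × [C(15,7) + 15 × C(15,6)]/C(30,7) = 2 × (6435 + 75075)/2035800 = 0.080.

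**Check by hand, 5% v 30%.** Boschloo's extra power comes almost entirely from these two tables. P(0 v 4) = 0.463 × 0.219 = 0.101 and P(1 v 6) = 0.366 × 0.147 = 0.054, together 0.155. The mixed rule's 28.0% plus 15.5 points gives 43.5%.

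**Power at 15 v 15 (all rates assumed).**

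| Event rates | Mixed rule | Boschloo | Loss (points) |
|---|---|---|---|
| 5% v 30% | 28.0% | 43.5% | 15.5 |
| 5% v 40% | 53.7% | 67.1% | 13.4 |
| 7% v 40% | 46.1% | 58.3% | 12.1 |
| 10% v 30% | 16.0% | 25.6% | 9.6 |
| 10% v 50% | 61.2% | 67.3% | 6.1 |
| 20% v 60% | 59.1% | 59.9% | 0.8 |
| 20% v 70% | 80.5% | 80.7% | 0.2 |

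Losses are taken from unrounded values.

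**At 20 v 20** the two regions no longer nest. Boschloo still gains for uncommon outcomes (5% v 30%: 47% to 54%) but is slightly less powerful for common ones (20% v 50%: 53% to 49%). There the mixed rule's higher power goes with a maximum size above 5%.

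**The case against.** Fisher's test never exceeds its nominal level, is conventional, and is used here on secondary outcomes for which the protocol claims no power. Choosing among 2×2 tests is detail often left to a statistical analysis plan, which may exist. All of this stands, and it is why the point is not an error in the plan.

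A reader might infer more: that all the categorical tests run at no more than 1.8%, with 11 to 15 points of power lost throughout. The protocol does not support that. Those figures describe Fisher's test on every table, whereas the plan also allows chi-square. Under the usual rule the maximum size is 4.3%, and for common outcomes the loss all but disappears.

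It is also fair to say that a better test rescues little where differences are modest. At 10% v 20%, power is about 4% with Fisher and 10% with Boschloo, so both are uninformative. Fifteen per arm is a floor, and the gain for uncommon outcomes shrinks with more evaluable women.

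Finally, a reader might infer that the choice of test is what tilts the trial towards a finding of equivalence. Conservatism adds to the number of non-significant results, but the main difficulty is that a difference test cannot show equivalence whichever 2×2 test is used. Replacing Fisher does not cure that; the interval for the risk difference helps with either test.

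**Conclusion.** The point holds for uncommon binary secondary outcomes at or near 15 evaluable women per arm. There the planned wording will in practice mean Fisher's test, and it gives up about 10 to 15 points of power against a test with the same guaranteed 5% ceiling. The loss is about 6 points at 10% v 50% and under 1 point at 20% v 60% or 20% v 70%.

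These sizes rest on the expected-count rule, the two-sided 5% level and the event rates, none of which the protocol states for these outcomes. They do not apply to outcomes with more than two categories, as type of delivery may have, or to repeated events counted within a woman.

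The analysis as planned is usable; this is an optional improvement in efficiency.

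**What to change.** For binary outcomes scored once per woman or once per infant (for example macrosomia, neonatal hypoglycemia, cesarean delivery yes/no), replace the choice between chi-square and Fisher with Boschloo's exact unconditional test at two-sided 5%. Report each with an exact unconditional 95% confidence interval for the risk difference, and name the interval method. The interval shows how large a difference the data cannot exclude, so that a non-significant result is not read as equivalence. A single named test also removes the unstated choice between tests and, at 20 per arm, the mixed rule's slight excess over 5%.

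The cost is a change of wording, slightly heavier computation and a test that is less familiar to clinical readers. No patients or data are added. Power for small differences stays low whichever test is used.

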**STUDY HYPOTHESIS**

Humalog® Mix50/50™ administered as 3 injections daily is equivalent to Humalog® plus Humulin N® insulin administered as 6 separate injections daily in terms of glucose control, but may have some advantages due to increased ease of use.

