**PRIMARY OBJECTIVE**

Compare the efficacy and safety of three daily injections of Humalog® Mix50/50™ to six daily injections of Humalog® and Humulin N® insulin, by fasting glucose measurements.

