## **ANTICIPATED FINDINGS**

We anticipate maternal and fetal outcomes with the Humalog® Mix50/50™ will be equivalent or non-inferior to standard insulin therapy due to the convenience of three injections rather than six per day. The risk of possible increased hypoglycemia, particularly during the night, however, needs to be carefully assessed.

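### The protocol hypothesises equivalence but makes equivalence the null of ordinary difference tests and gives no margin, so the planned tests cannot establish it

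*Protocol*

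**What the plan says.** Four sections of the protocol bear on this.

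- **Study Hypothesis:** the claim about glucose control is that "Humalog® Mix50/50™ administered as 3 injections daily is equivalent to Humalog® plus Humulin N® insulin administered as 6 separate injections daily".
- **Anticipated Findings:** maternal and fetal outcomes "will be equivalent or non-inferior to standard insulin therapy".
- **Statistical Analysis:** continuous variables, glucose among them, "will be compared with t-tests and potential confounders (age, race/ethnicity etc.) will be controlled for with linear regression"; categorical variables get chi-square or Fisher's tests. The section closes: "Our tests will be testing the hypothesis that the two treatments are different and the null hypothesis will be equivalence".
- **Sample Size:** 15 evaluable women per arm "will have 80% power to find an inter-group difference as small as 8 mg/dL at a p-value of 0.05".

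The Primary Objective is neutral: "Compare the efficacy and safety of three daily injections" with six, by fasting glucose. No section gives an equivalence or non-inferiority margin, or a rule that sets a confidence interval against one. The 8 mg/dL is a difference to be detected and is never called a margin.

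**The concern.** The claim that the trial hopes to support has been placed in the null hypothesis. Rejecting that null shows that the regimens differ. Failing to reject it shows only that the data did not separate them, which may mean that they are alike or that the trial was too small or too noisy.

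A reader who takes the Study Hypothesis and the statement of the null together is invited to treat a non-significant p-value as confirmation. The probability of calling truly different regimens equivalent is then not held at 5%. When a true difference exists, that probability rises as the trial gets smaller or the measurements noisier, so a weaker trial makes the favourable conclusion easier to reach. Fasting glucose is the primary measure, so the headline conclusion is affected.

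**Working it through.** **Inputs.** From Sample Size: n = 15 per arm, detectable difference 8 mg/dL, power 80%, significance level 0.05. Not given: a numerical standard deviation (SD), whether the test is one- or two-sided, and a margin.

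**1. The plan's own figure.** The 80% cannot be checked independently without an SD, but it can be solved backwards. With the noncentral t on 28 degrees of freedom and noncentrality 8 / (SD × √(2/15)), 80% power requires
- SD = 7.55 mg/dL for a two-sided 5% test;
- SD = 8.60 mg/dL for a one-sided 5% test.

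The main figures below use 7.55.

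**2. Precision.** The standard error of the difference is 7.55 × √(2/15) = 2.76 mg/dL. The 95% half-width at that SD is 2.048 × 2.757 = 5.65 mg/dL. An observed difference of 5 mg/dL would therefore have a 95% interval of about −0.65 to 10.65. It is non-significant, yet it includes the 8 mg/dL that the trial was sized to find.

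**3. How often the planned test is non-significant (two-sided 5%).**

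| Scenario | True difference 8 | True difference 5 |
|---|---|---|
| 15 per arm, SD 7.55 | 20% | 58% |
| 15 per arm, SD 8.60 | 31% | 66% |
| 15 per arm, SD 12 (assumption) | 58% | 80% |
| 10 per arm (assumption), SD 7.55 | 39% | 71% |

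With no true difference the rate is 95% whatever the size or SD. The SD 8.60 row shows a two-sided analysis of a trial that was sized one-sided. A matching one-sided test would miss 8 mg/dL 20% of the time by construction.

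**4. Non-significant but uninformative.** By simulation (2,000,000 trials, true difference 5, SD 7.55, 15 per arm), about 40% of trials are non-significant and also have an upper 95% limit above 8 mg/dL.

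**5. What a margin rule would do.** Take 8 mg/dL as the margin (assumption) and a true difference of exactly 8. Non-inferiority judged on the two-sided 95% interval is falsely claimed 2.5% of the time. Equivalence judged by two one-sided 5% tests (90% interval) is falsely claimed 5% of the time. Non-significance as the criterion gives 20%.

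**6. Power of a margin rule at the planned size.** The margins are assumptions, and there is no true difference unless stated.

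| Rule, 15 per arm | Power | n per arm for 80% |
|---|---|---|
| Non-inferiority (one-sided 2.5%), margin 8, SD 7.55 | 80% | 15 |
| Same, true difference 2 mg/dL | 56% | – |
| Non-inferiority, margin 5, SD 7.55 | 42% | 37 |
| Non-inferiority, margin 8, SD 12 | 42% | 37 |
| Equivalence, 90% interval, margin 8, SD 7.55 | 76% | 16 |
| Equivalence, 95% interval, margin 8, SD 7.55 | 60% | 20 |

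The first row equals the stated 80% because a one-sided 2.5% test against a margin of 8 at zero difference is almost the same calculation as a two-sided 5% test for a difference of 8.

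**The case against.** The strongest reply is that the operative sections agree with one another. The Primary Objective says compare, Sample Size is built to find a difference, and Statistical Analysis tests for a difference. Nowhere does the protocol say that a non-significant p-value will be read as equivalence, and Anticipated Findings is an expectation, not a decision rule. The error rates above therefore measure a reading that the protocol invites but does not prescribe. A result significantly in favour of Mix50/50 would also validly support non-inferiority without a margin. Finally, an unseen SAP might supply an interval rule.

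Part of this stands. The rates are conditional on that reading, and the gap in principle is complete for equivalence but only partial for non-inferiority. The objection does not remove the contradiction, however. The one sentence headed as the study hypothesis claims equivalence, and the protocol itself fixes equivalence as the null. That is a stated rule pointing the wrong way for the claim, not a detail left open, and an SAP could repair it only by contradicting the protocol.

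A further caution is fair. The 2.5% and 5% error rates assume complete, unselected outcomes. Methods discontinues women on criteria that include persistently raised fasting glucose, in terms written around the Mix50/50 arm. If those women are not evaluable, no margin rule guarantees these rates.

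**Conclusion.** The concern holds and must be fixed before the primary comparison can be interpreted. The planned tests can show that the regimens differ; they cannot establish the stated equivalence. If non-significance were taken as support, a true difference of 8 mg/dL would pass as equivalent in about 20% of trials and one of 5 mg/dL in about 58%.

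Those sizes rest on 15 evaluable women per arm, a two-sided 5% t-test and the back-solved SD of 7.55 mg/dL; they grow with a larger SD or fewer women. The logical point needs none of these figures. The stated 80% power is neither confirmed nor refuted. The defect lies mainly in the hypothesis and the missing margin: the sample size falls well short only with a margin tighter than 8 mg/dL, a larger SD or a true difference away from zero.

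**What to change.** Choose one of two routes.

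**Margin route.** Replace the closing sentence of Statistical Analysis with:

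> For the primary comparison of fasting glucose, the null hypothesis is that the Mix50/50 minus standard difference is at least the pre-specified margin (upward only for non-inferiority; in either direction for equivalence). The difference will be reported with its confidence interval (two-sided 95% for non-inferiority; 90% for equivalence by two one-sided 5% tests). Non-inferiority will be concluded only if the upper limit is below the margin, or equivalence only if the whole interval lies within plus or minus the margin. A non-significant difference test alone will be reported as inconclusive. Hypoglycemia and the other secondary outcomes will be tested for a difference and reported with confidence intervals; no equivalence will be concluded from them.

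In addition:
- Keep only the chosen option, equivalence or non-inferiority, and use the same term in Study Hypothesis, Statistical Analysis and Anticipated Findings.
- Narrow Anticipated Findings to fasting glucose. It now extends the expectation to all maternal and fetal outcomes, while also saying "The risk of possible increased hypoglycemia, particularly during the night, however, needs to be carefully assessed".
- State and justify the margin, no wider than the 8 mg/dL used for sizing; a wider one would accept as equivalent a difference that the trial was designed to detect.
- Say whether the t-test or the adjusted regression supplies the deciding interval.
- Restate the power in Sample Size with a numerical SD, without assuming that 80% carries over.

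The cost is wording in four sections and possibly more women: none or a few per arm at margin 8 and SD 7.55 with no true difference, but about 37 per arm for non-inferiority at margin 5 or SD 12.

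**Comparison-only route.** Reword Study Hypothesis and Anticipated Findings as a comparison reported with a confidence interval, in line with the Primary Objective, and make no equivalence claim. This changes wording only, but it gives up the equivalence conclusion.

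On the margin route the sponsor must accept that the trial may end inconclusive and that the restated power may look less favourable.

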## **ANTICIPATED FINDINGS**

We anticipate maternal and fetal outcomes with the Humalog® Mix50/50™ will be equivalent or non-inferior to standard insulin therapy due to the convenience of three injections rather than six per day. The risk of possible increased hypoglycemia, particularly during the night, however, needs to be carefully assessed.

